Patients who experience a DLT will be allowed to remain on study if they meet the following criteria: (1) the Investigator believes it is appropriate for patients to remain on study; (2) the event has resolved and no longer meets the definition of DLT; and (3) the timeline for resolution falls within the guidelines for dose delays ([Section 8.4](#)).

Patients who complete C1 may continue on study as long as, in the Investigator's judgment, the patient is tolerating study treatment, is not at an increased safety risk, and continues to meet protocol eligibility criteria.

After completion of the Dose Escalation/Confirmation Phase of the study, with identification of the MTD or RP2D, the Phase 2 portion of the study will commence.

**Phase 2 (Expansion):** In the Expansion Phase, entinostat in combination will be evaluated using the RP2D identified in the Dose Escalation/Confirmation Phase. Up to 4 Expansion Cohorts consisting of distinct subsets of patients with solid tumor cancers may be explored. Each cohort evaluated during the Expansion Phase will employ a Simon 2-stage design. The final decision about which Expansion Cohorts to study will be based on data from the Dose Escalation/Confirmation Phase, emerging clinical data from other studies, and/or nonclinical data. Expansion cohorts may include:

1. Cohort 1: NSCLC, with squamous cell or adenocarcinoma histology who have not been treated with a PD-1 or PD-L1 blocking antibody

 Depending upon emerging data, the Sponsor may elect, instead of histology, to evaluate NSCLC consisting of PD-1+ and PD-L1+ NSCLC patients. In this case, the protocol will be amended accordingly.

2. Cohort 2: Patients with NSCLC (any histology) who have previously been treated with and unequivocally progressed on either a PD-1 or PD-L1-blocking antibody
3. Cohort 3: Patients with melanoma who have previously been treated with and unequivocally progressed on either a PD-1 or PD-L1-blocking antibody (i.e., pembrolizumab, nivolumab, MEDI4736, or GNE PDL1 [MPDL3280A])
4. Cohort 4: Patients with CRC (mismatch repair-proficient) who have not been previously treated with a PD-1 or PD-L1 blocking antibody

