#### 12.1.2 Expansion Phase

In the Expansion Phase of the study, the safety and preliminary antitumor activity of entinostat when administered at the RP2D with pembrolizumab will be explored in up to 4 cohorts of adult solid tumors as previously defined. Up to 252 patients are planned to be enrolled among the 4 cohorts. Patients will be enrolled in each cohort according to a single-arm study design with ORR, as determined by irRECIST, as the primary endpoint. The Expansion Phase will be carried out in 2 stages so that enrollment for 1 or more of the cohorts evaluated can terminate early in the event the antitumor activity of the combination regimen is not sufficient. The decision to terminate or continue enrollment for each cohort will be made independently of the other. The number of patients evaluated in each stage and the minimum number of responders needed to continue to the next stage, as described for cohort 1, was determined based on the optimum version of Simon's 2-stage design ([Simon 1989](#)), with 80% power and 1-sided significance level of 10%. For cohort 4, the number of patients evaluated in each stage and the minimum number of responders needed to continue to the next stage was determined based on the optimum version of Simon's

2-stage design, with 90% power and 1-sided significance level of 5%. For cohorts 2 and 3, the number of responders needed to declare the study a success was based on single proportion binomial test with 90% power and 1-sided significance level of 5%. Note that the protocol may be amended to allow for enrollment of additional or different cohorts, for example, patients with PD-L1-positive NSCLC, based on emerging data during study conduct.

Syndax will conduct one administrative analysis when at least 60% (42 out of 70 patients in cohort 2, 31 out of 52 patients in cohort 3) of patient information have accrued in cohorts 2 and 3 for decision making for late phase development planning. This administrative look will not lead to stopping of the study. Nonetheless, 0.01 alpha is being allocated to spend for the first administrative look and leaving 0.04 alpha for the final analysis.

***Cohort 1 (NSCLC patients with squamous cell and adenocarcinoma histology who have not been previously treated with a PD-1 or PD-L1-blocking antibody)***

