1 INTRODUCTION

Clinical Trial SNDX-275-0601 is an open-label Phase 1b/2 evaluating the combination of entinostat with pembrolizumab in patients with advanced metastatic or recurrent NSCLC, melanoma, or mismatch repair-proficient colorectal cancer. The study has 2 phases, a Dose Escalation/Confirmation Phase (Phase 1b) and an Expansion Phase (Phase 2), with the Expansion Phase utilizing a Simon 2-stage design ([Simon 1989](#)) for each cohort. An additional cohort (Entinostat Monotherapy Immune Correlate [EMIC] Cohort) evaluating single agent entinostat followed by the combination will also be evaluated in patients with NSCLC in the Phase 2 expansion phase.

This SAP contains a detailed description of the data presentations and statistical analyses that will be included in the clinical study report for Protocol SNDX-275-0601. The statistical methods and analyses described here are based on those presented in the study protocol. Any changes made to the planned analyses after this document has been finalized will be noted in the clinical study report.

This version of the SAP was written in accordance with the following protocol versions:

Table 1-1 **Protocol Versions**

Protocol	Version Date
Original	08-April-2015
Amendment #1	05-June-2015
Amendment #2	04-April-2016
Amendment #3	23-February-2017
Amendment #4	25-August-2017
Amendment #5	12-April-2018

The first patient was enrolled under the original protocol dated 08-April-2015. Since then, study 601 has undergone 5 amendments (Table 1).

For Amendment #1, significant changes include, addition of exploratory endpoint, the clarification of duration of therapy, clarification of the number of patients enrolled, modification of the language to include a definition of a DLT-evaluable patient, and the definition of DLT.

Amendment #2 clarified the process of deciding on the Recommended Phase 2 Dose (RP2D), updated the Adverse Events terms of attribution/relatedness, updated the dose modification requirements for entinostat.

Amendment #3 added an additional cohort of patients: Mismatch Repair-Proficient Colorectal Cancer and updated pembrolizumab background information

Amendment #4 increased the sample size for Cohorts 2 and 3 and modified the corresponding statistical considerations accordingly (Section 12 of the protocol), removed Proton Pump Inhibitors (PPIs) from the list of medications to be avoided, and modified Eligibility Criteria to clarify prior disease progression on immunotherapy.

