In the Expansion Phase of the study, the safety and preliminary antitumor activity of entinostat when administered at the RP2D with pembrolizumab will be explored in up to 4 cohorts of adult solid tumors as previously defined. Up to 252 patients are planned to be enrolled among the 4 cohorts. Patients will be enrolled in each cohort according to a single-arm study design with ORR, as determined by irRECIST, as the primary endpoint. The Expansion Phase will be carried out in 2 stages so that enrollment for 1 or more of the cohorts evaluated can terminate early in the event the antitumor activity of the combination regimen is not sufficient. The decision to terminate or continue enrollment for each cohort will be made independently of the other. The number of patients evaluated in each stage and the minimum number of responders needed to continue to the next stage, as described for cohorts 1, 2 and 3, was determined based on the optimum version of Simon's 2-stage design ([Simon 1989](#)), with 80% power and 1-sided significance level of 10%. For cohort 4, the number of patients evaluated in each stage and the minimum number of responders needed to continue to the next stage was determined based on the optimum version of Simon's 2-stage design, with 90% power and 1-sided significance level of 5%.

Cohort 1 (NSCLC patients with squamous cell and adenocarcinoma histology who have not been previously treated with a PD-1 or PD-L1-blocking antibody)

A maximum of 46 patients will be enrolled in Cohort 1. A true ORR of 35% is hypothesized. An ORR greater than 20% is considered a lower threshold for antitumor activity that would warrant continued development. Based on the design elements specified above, up to 13 patients may be enrolled for either tumor type during the first stage; if 2 or fewer patients achieve an objective response (CR or PR), confirmed or unconfirmed, then enrollment will terminate; otherwise, 33 additional patients will be enrolled during the second stage. Upon completion of the second stage, if 13 or more patients out of the 46 enrolled achieve CR or PR, then the true ORR for the combination therapy likely exceeds 20%, the lower threshold of acceptable antitumor activity. Alternatively, if 12 or fewer patients achieve an objective response at the end of the second stage, then the true ORR is likely 20% or lower, and further evaluation of the

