combination therapy may not be pursued for that tumor type. If the true ORR is 20% or less for a tumor type, then the expected sample size is 29.4, with probability of terminating enrollment at the end of the first stage equal to 50%.

Cohort 2 (Patients with NSCLC (any histology) who have previously been treated and progressed on a PD-1 or PD-L1-blocking antibody)

A maximum of 56 patients will be enrolled in Cohort 2. A true ORR of 15% is hypothesized. A response rate greater than 5% is considered the lower threshold for antitumor activity that would warrant continued development in this setting. Based on the design elements specified above, up to 20 patients may be enrolled during the first stage: if 1 or no patients achieve a CR or PR, confirmed or unconfirmed then enrollment will terminate; otherwise 36 additional patients will be enrolled during the second stage. Upon completion of the second stage, if 5 or more patients out of 56 enrolled achieve CR or PR, then true ORR for the combination regimen likely exceeds 5%, the lower threshold of acceptable antitumor activity. Alternatively, if 4 or fewer patients achieve an objective response at the end of the second stage, then the true ORR is likely 5% or lower and further evaluation of the combination therapy may not be pursued in this setting. If the true ORR is 5% or less, then the expected sample size is 29.5, with probability of terminating enrollment at the end of the first stage equal to 74%. However, with Amendment 5, the study design for this cohort is changed from Simon 2-stage design to single proportional binomial test after moving in to 2nd stage. Based on single proportional binomial test, maximum of 70 patients are enrolled in Cohort 2.

Ninety-six percent 1-sided confidence interval (or 92% 2-sided confidence interval) of the observed one sample proportion will be calculated. The trial will be considered a success if the lower limit of 96% confidence interval is greater than 5%.

Syndax will conduct one administrative analysis when at least 60% (42 out of 70 patients) of patient information has been accrued in cohort 2 for decision making for late phase development planning. This administrative look will not lead to stopping of the study. Nonetheless, 0.01 alpha is being allocated for the first administrative look, leaving 0.04 alpha for the final analysis.

Cohort 3 (Patients with melanoma who have previously been treated and progressed on a PD-1 or PD-L1-blocking antibody)

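### Cohorts 2 and 3: the stated 90% power and 5% alpha leave out the Simon Stage 1 gate that both cohorts had to pass before the single-proportion test

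*SAP*

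**What the plan says.** SAP 2.3.1 first sets out a Simon design for each cohort. For Cohort 2, "up to 20 patients may be enrolled during the first stage: if 1 or no patients achieve a CR or PR, confirmed or unconfirmed", enrolment stops. The final rule was met "if 5 or more patients out of 56 enrolled achieve CR or PR", and at a true ORR of 5% "the expected sample size is 29.5, with probability of terminating enrollment at the end of the first stage equal to 74" per cent. Cohort 3 has the same structure: 13 patients in Stage 1, stop at 1 or fewer responses, final rule 6 of 34.

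The same paragraphs then say that "the study design for this cohort is changed from Simon 2-stage design to single proportional binomial test after moving in to 2nd stage", with maxima of 70 and 52. Success is a 96% one-sided lower limit above 5% (Cohort 2) or 10% (Cohort 3). The only alpha allowance is 0.01 for the administrative look, leaving 0.04 for the final test. Protocol 12.1.2 says that the number of responders needed in these cohorts "was based on single proportion binomial test with 90% power and 1-sided significance level of 5" per cent.

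Other text has not caught up. SAP 2.3.1 still says that the stage sizes, "as described for cohorts 1, 2 and 3, was determined based on the optimum version of Simon's 2-stage design", at 80% power and 10% alpha. Protocol 5.1 opens by limiting the Simon design to Cohorts 1 and 4, then says: "Each cohort evaluated during the Expansion Phase will employ a Simon 2-stage design".

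The intervals also differ. SAP 3.8 gives a 95% interval for every cohort, adjusted for the multistage design, plus a 92% interval for Cohorts 2 and 3. Protocol 12.4.5 gives the adjusted interval to Cohorts 1 and 4 only, and a 98% interval to Cohorts 2 and 3.

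**The concern.** Neither document says in words that Stage 1 patients count in the final test, but a cohort maximum of 70 or 52 with one crude proportion implies it. The procedure as run is therefore a gate followed by a pooled test, while the stated error rates belong to a single fixed sample.

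This matters in two ways. A futility gate removes some truly active cohorts, so power counted from the start is lower than for the same cut-off without a gate. And a cohort that survives the gate carries a Stage 1 response rate that was selected to be high, which feeds into the pooled ORR and test. The SAP says these cohorts inform late-phase planning, so readers need to know which error rates apply to a result such as 8 of 70.

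**Working it through.** **Inputs** (SAP 2.3.1 and Protocol 12.1.2). Cohort 2: n1 = 20, continue if X1 ≥ 2, N = 70, p0 = 0.05, p1 = 0.15. Cohort 3: n1 = 13, continue if X1 ≥ 2, N = 52, p0 = 0.10, p1 = 0.25. Final one-sided level 0.04, stated power 90%. The interval method is not named; exact (Clopper-Pearson) limits are assumed here and varied in step 6.

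**1. Reproduce the plan's figures.**
- Cohort 2 early stopping at p0: 0.95^20 + 20 × 0.05 × 0.95^19 = 0.736 (stated 74%). Expected size: 20 + 36 × 0.264 = 29.5 (stated 29.5).
- Cohort 3: 0.9^13 + 13 × 0.1 × 0.9^12 = 0.621 (stated 62%). Expected size: 13 + 21 × 0.379 = 20.95 (stated 20.9).
- The Simon rules deliver alpha 9.7% and 9.6% and power 80.1% and 81.1%, so the 80%/10% text is right for that design.
- N after the switch, from n = [(z(0.96)√(p0(1−p0)) + z(0.90)√(p1(1−p1))) / (p1−p0)]². Cohort 2: [(1.751 × 0.218 + 1.282 × 0.357)/0.10]² = 70.4 (stated 70). Cohort 3: [(1.751 × 0.300 + 1.282 × 0.433)/0.15]² = 51.9 (stated 52). At one-sided 0.05 the formula gives 66.6 and 48.8, so 0.04 was the level used. It has no Stage 1 term.

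**2. Cut-off.** The exact 96% lower limit is 4.6% for 7/70 and 5.6% for 8/70; it is 9.0% for 9/52 and 10.4% for 10/52. Success therefore needs 8/70 or 10/52.

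**3. Error rates.** Without the gate: P(X ≥ c). From the start: P(X1 ≥ 2 and X ≥ c), summed exactly over X1. Given passage: that value divided by P(X1 ≥ 2), which is 0.264 at the null and 0.824 at the alternative for Cohort 2, and 0.379 and 0.873 for Cohort 3.

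| | Cohort 2, 8/70 | Cohort 3, 10/52 |
|---|---|---|
| Type I, no gate | 2.3% | 3.2% |
| Type I, from the start | 1.8% | 2.6% |
| Type I, given passage | 6.7% | 6.8% |
| Power, no gate | 84.3% | 87.1% |
| Power, from the start | 73.7% | 78.9% |
| Power, given passage | 89.4% | 90.4% |

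**4. Share due to the gate.** The gap from 90% to 84.3% and 87.1% comes from the normal approximation and integer cut-off. The gate accounts for the rest: about 10.6 points in Cohort 2 and 8.1 in Cohort 3. At the hypothesised ORR the gate alone stops a cohort 17.6% and 12.7% of the time.

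**5. Bias in the crude ORR given passage.** E[X1 | X1 ≥ 2] at the null is 2.357 and 2.464.
- Cohort 2: (2.357 + 50 × 0.05)/70 = 6.9% for a true 5%.
- Cohort 3: (2.464 + 39 × 0.10)/52 = 12.2% for a true 10%.
- At the hypothesised ORR the values are 15.7% for a true 15% and 25.7% for a true 25%.

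**6. Other interval methods.** Score limits need 7/70 and 9/52: type I error is 4.2% and 5.4% from the start, and 15.9% and 14.4% once Stage 1 is passed; power from the start is 78.5% and 83.3%. Wald limits need 9/70 and 11/52: type I error is 2.5% and 2.8% once Stage 1 is passed, but power is 66.2% and 72.2% from the start and 80.4% and 82.7% once Stage 1 is passed.

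**The case against.** Much can be said for the plan, and several stronger readings fail.

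- *Reuse of Stage 1 patients inflates type I error.* A reader might infer this, but the gate can only stop for futility and so lowers it, from 2.3% to 1.8% and from 3.2% to 2.6%. Pooling Stage 1 patients is how Simon designs work; Cohorts 1 and 4 do the same.
- *There is no allowance anywhere.* SAP 3.8 adjusts a 95% interval for the multistage design in each cohort, which on its wording includes Cohorts 2 and 3. The gap is narrower: the interval that decides success and the crude ORR carry no stated adjustment, and the protocol limits the adjusted interval to Cohorts 1 and 4.
- *The conditional rates show a fault special to the switch.* They do not. The same measure gives 19.4% for Cohort 1 and 17.1% for Cohort 4, and 36.6% and 25.3% for the Simon rules that Cohorts 2 and 3 left behind, so the switch tightened the test. Cohort 4's expected crude ORR given passage is 7.0% at a true 5%, close to Cohort 2's 6.9%.
- *The whole shortfall from 90% is the gate.* Step 4 shows that part of it is the cut-off.
- *The dating shows an undisclosed, data-driven change.* SAP 2.3.1 ties the switch to Amendment 5, while the SAP introduction says "Amendment #4 increased the sample size for Cohorts 2 and 3 and modified the corresponding statistical considerations accordingly". That is an amendment summary; the difference is clerical and says nothing about what data had been seen.

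It is also fair that power given passage is close to 90%, which may be what was meant for cohorts already in Stage 2. But the plan does not say so, and on that basis type I error under exact limits is 6.7% and 6.8% against the 4% final level.

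**Conclusion.** The point stands in limited form. On either consistent basis one stated figure is not delivered. From the start, alpha is held but power is 73.7% and 78.9% rather than 90%. Given passage, power is about 90% but type I error exceeds the final level of 4%. The upward bias in the crude ORR given passage is 1.9 and 2.2 points at the null and about 0.7 points at the hypothesised ORR: worth reporting, not large. This should be corrected, but it does not undermine the cohorts.

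The figures rest on four conditions.
- Exact limits are used. Under score or Wald limits the numbers move, but power from the start stays below 90%.
- The switch and the new N did not depend on response data, which the documents do not address. As an outer bound, allowing success by either the Simon rule or the new rule gives type I error of 9.7% and 9.9%.
- The administrative look is not a route to success. If it were, type I error from the start would be 1.9% and 2.8%.
- The gate counts unconfirmed responses, so the figures that involve it are approximate if the final ORR requires confirmation.

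**What to change.** - In SAP 2.3.1 and Protocol 12.1.2, restate type I error and power for Cohorts 2 and 3 with the gate included. Say whether each figure is counted from the start or given passage, name the interval method, say that Stage 1 patients are counted, and say what data had been seen at the switch.
- Beside the crude ORR, report either a multistage-adjusted estimate or the ORR with an exact interval in the post-gate patients (70 − 20 = 50 and 52 − 13 = 39), whom the gate does not bias.
- Reconcile SAP 3.8 with Protocol 12.4.5 on which cohorts get the adjusted 95% interval and on 92% versus 98% for Cohorts 2 and 3.
- Keep the 80%/10% Simon text for Cohorts 2 and 3 but label it as the superseded design, since it is the source of the gate. Correct the later sentence in Protocol 5.1 that applies the Simon design to every cohort, and the matching statements in SAP 1 and 2.3.

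The cost is wording and one extra ORR line per cohort. No further patients or data are needed. The stated power becomes less favourable if it is counted from the start.

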2.3.2 Estimated Treatment and Study Duration

The maximum duration of treatment for this study is planned to be 35 cycles (approximately 2 years.)

Patients who complete C1 may continue on study as long as, in the Investigator's judgment, the patient is tolerating the study treatment, is not at an increased safety risk, and continues to meet protocol eligibility criteria.

If a patient permanently discontinues 1 of the 2 study drugs (either entinostat or pembrolizumab), the patient may continue to receive monotherapy for up to 2 years, unless alternate therapy is started or another discontinuation criterion is met (Section 10 of the protocol).

Patients who discontinue both study drugs will receive standard of care outside the auspices of this study at the Investigator's discretion.

After discontinuation of both study drugs, patients will complete an EOT visit within 7 days (+/- 3 days) after the last study drug dose and Safety Follow-up visits 30 days (+/- 3 days) and 90 days (+/- 3 days) thereafter. After completion of the 30-day Safety F/U visit, patients who have not experienced PD are to be followed every 2 months until PD and every 3 months thereafter until death or closure of the study by the

Sponsor. The purpose of the post-treatment follow-up is to ascertain the duration of PFS for all patients in the study. After development of PD, surviving patients are to be followed on an every 3-month basis for alternate therapy and survival until closure of the study. Up to approximately 40 study centers are planned to be recruited for participation in this study.

2.3.3 Study Drug Treatment

Entinostat

Patients will receive entinostat in an open-label fashion; the dose for an individual patient is dependent on the cohort/study phase in which the patient is enrolled (Section 8.2.1.1 of the protocol).

The dose of entinostat is dependent on the cohort / study phase in which the patient is enrolled. In the Dose Escalation Phase, the planned entinostat doses to be investigated are:

- 3 mg weekly
- 5 mg weekly

In the Dose Confirmation Phase, 9 patients will receive entinostat at the prospective MTD/RP2D identified in the Dose Escalation Phase.

All patients will self-administer entinostat at the assigned dose and regimen PO. On study days on which patients receive both entinostat and pembrolizumab, entinostat is to be taken prior to pembrolizumab.

Pembrolizumab

The pembrolizumab treatment to be used in this study is outlined in Table 2-1.

Table 2-1**Study Treatment**

Drug	Dose/Potency	Dose Frequency	Route of Administration	Regimen	Use
Pembrolizumab	200 mg	Every three weeks (Q3W)	Intravenous (IV)	Day 1 of each cycle (3-week cycles)	Experimental

Pembrolizumab treatment will begin on C1D1. Pembrolizumab will be administered on D1 of each 3-week treatment cycle after all procedures and assessments have been completed as detailed on the Schedule of Study Assessments (Table 1-1 of the protocol or, for the EMIC cohort Table 1-2 of the protocol).

Pembrolizumab will be administered as a dose of 200 mg using a 30-minute IV infusion. Sites should make every effort to target infusion timing to be as close to 30 minutes as possible. However, given the variability of infusion pumps from site to site, a window between -5 minutes and +10 minutes is permitted (i.e., infusion time is 30 minutes -5 min/+10 min).

